7.2 STOPPING CRITERIA

STOPPING CRITERIA

We propose as a stopping criterion the occurrence of 1 case or more of esophageal laceration based on the finding of the Barium Swallow.

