- The balloon is positioned in the appropriate location with the distal marker band at the level of the lower esophageal sphincter.
- The balloon is inflated with contrast medium with 4-8 ATM of pressure as indicated on the Inflation Syringe (Figure-3).

Deflation and Withdrawal:

- The balloon is deflated prior to withdrawing from the esophagus.
- The deflated DV8 Retractor Balloon is withdrawn from the esophagus using a smooth, gentle, steady motion.

Figure-3: X ray images of the DV8 retractor before and after inflation.

Preliminary data:

The esophagus was successfully displaced using the DV8 retractor in over 200 patients worldwide. Eleven cases have been performed at MGH. No complications have been reported with its use. In a cohort study at Mt. Sinai Medical Center in New York, 47 patients underwent esophageal deviation using the DV8 tool and were compared with 114 patients who underwent deviation using the off-the-shelf stylet. All procedures were performed under general anesthesia. The extent of deviation, as measured by the distance between the trailing edge of the esophagus and the ablation points, was significantly larger with the DV8 tool (Figure-4). Moreover, the incidence of esophageal temperature rises was higher with the off-the-shelf technique compared to the DV8 retractor (Figure-5). Another preliminary study was conducted by the Mt-Sinai group in order to assess the optimal distance for esophageal movement that eliminates the chance of heating. It showed that if the esophagus is moved by an average of 2 cm from the ablation site, no significant heating occurs (Figure-6)

Figure-4: Comparison of the extent of deviation between the DV8 retractor and off-the-shelf stylet.

[figure not shown]

Figure-5: Comparison of the incidence of esophageal temperature rise between the DV8 retractor and the off-the-shelf stylet.

[figure not shown]
[figure not shown]

Figure-6: Incidence of esophageal temperature rise at different distances from the area of ablation.

These data demonstrate the feasibility and safety of the novel technique of esophageal deviation that facilitates uninterrupted energy delivery to the posterior wall during AF. It also demonstrated that the esophagus needs to be moved by an average of 2 cm in order for heating not to occur. Although the results have been very encouraging with respect to safety and efficacy, we believe that there is value in an additional study to prove the reproducibility of the findings.

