5.2 SECONDARY CLINICAL ENDPOINTS

The following secondary endpoints will be assessed:

1. The extent of esophageal deviation as measured by the incidence of successfully moving the esophagus by an average of 2 cm from the ablation line for the ipsilateral PV pairs.
2. The incidence of esophageal laceration as assessed by a Barium swallow study performed within 1-3 days of the procedure.
3. Incidence of PV reconnection at 30 min post-ablation
4. Fluoroscopy time
5. Procedure duration
6. Time from start of ablation to last ablation lesion for pulmonary vein isolation

The deviation distance was based on the preliminary study mentioned above, showing that if the esophagus is moved by an average of 2 cm, no significant heating occurs.

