9.3.2 SERIOUS ADVERSE EVENTS

Serious adverse events are defined as any experience that results in a fatality or is life threatening; results in significant or persistent disability; or represents other significant hazards or potentially serious harm to research subjects or others, in the opinion of the investigators.

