9.3.4 CAUSALITY

The investigator will assess the relationship of an adverse event to the intervention. The investigator should distinguish the relationship between the event and (a) ablation procedure (i.e. AF ablation procedure or other concomitant procedures), and (b) the esophageal deviation. Causality will be defined as follows:

Probable

Adverse events that, after careful medical evaluation, are considered with a high degree of certainty to be related to the intervention (AF ablation ± esophageal deviation). The following characteristics will apply:

- A reasonable temporal relationship exists between the event and the intervention, and
- The event is a known reaction to the intervention, and cannot be explained by an alternative etiology commonly occurring in the population/individual.

Possible

Adverse events that, after careful medical evaluation, do not meet the criteria for a probable relationship to the intervention, but for which a connection cannot be ruled out with certainty. The following characteristics will apply:

- The event occurs after intervention, and
- The event is not a known reaction to intervention, but cannot be explained by a commonly occurring alternative etiology

Unlikely

Adverse events that, after careful medical evaluation, do not meet the criteria for a possible or probable relationship to intervention and for which a connection is unlikely. The following characteristics will apply:

- The event does not follow a reasonable temporal sequence from administration of the intervention, or
- May have been produced by environmental factors, and there is no apparent pattern of response to the intervention.

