9.4 RISKS

As the protocol described is standard to an AF ablation procedure, the risks of the procedure include that of a standard AF procedure, which are:

Common:

- Discomfort at the site of venous access
- Groin hematoma

Uncommon:

- Discomfort in the throat region
- Cardiac Perforation requiring drainage or surgery
- Pulmonary venous stenosis / occlusion
- Thrombus formation / stroke
- Injury to adjacent structures (phrenic nerve, esophagus, lung, cardiac valves)
- Bleeding

- Congestive heart failure
- Renal dysfunction
- Vascular complications (including pseudoaneurysm, AV fistula requiring surgical intervention)
- Myocardial infarction
- Esophageal deviation risks include dental injury and esophageal injury similar to that of TEE
- Radiation burns
- Ventricular arrhythmias or QT prolongation
- Pneumonia and/or sepsis
- Anaphylaxis
- Death

Additional risks unique to the protocol are

- Sore throat
- Aspiration pneumonia from barium sulfate or Gastrografin.
- Difficulty or painful swallowing
- Bleeding from the mouth area or from the food pipe
- Perforation—a tear or hole in the esophagus (the “tube” that connects your mouth to your stomach”) or heart
- Infection
- Failure to protect the esophagus from heat related injury.
- Nausea
- Abdominal pain
- Atrio-esophageal fistula- An abnormal connection between the atria of the heart and the esophagus in which they fuse together

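### The only study-level stopping rule needs a laceration on barium swallow, so it misses a laceration or perforation confirmed only by another method, and an atrio-esophageal fistula

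*Combined protocol and SAP*

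**What the plan says.** Section 7.2 is a single sentence: "We propose as a stopping criterion the occurrence of 1 case or more of esophageal laceration based on the finding of the Barium Swallow". Neither the rest of the protocol nor the Appendix 2 flow sheet contains another rule that stops or pauses the study. The Appendix 2 instruction about an esophageal diverticulum keeps one patient from deviation; it does not halt enrolment.

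The same test defines a secondary endpoint in section 5.2: "The incidence of esophageal laceration as assessed by a Barium swallow study performed within 1-3 days of the procedure". Section 9.2.1 schedules one swallow per patient, the next day if possible and by day 3 at the latest. Section 7.2 itself names no day.

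Among the risks that section 9.4 lists as unique to the protocol are perforation, described as "a tear or hole in the esophagus" or heart, and "Atrio-esophageal fistula- An abnormal connection between the atria of the heart and the esophagus". The introduction (section 4) says that a fistula presents late, usually within two weeks, and is often fatal.

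Other safety provisions act on the patient or on reporting:

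- Section 9.2.3: a visualized injury leads to a proton pump inhibitor, chest CT and gastroenterology referral.
- Section 9.2.2: the swallowing score is repeated by telephone at 2 weeks and 3 months.
- Section 9.3: the principal investigator oversees safety, and adverse events go to the IRB.
- Section 9.3.4: "The investigator should distinguish the relationship between the event and (a) ablation procedure" and, separately, the deviation.
- Section 9.3.5: unanticipated problems are reported within 5 working or 7 calendar days.

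**The concern.** The plan has already decided that one laceration is enough to stop. That decision is tied to one kind of injury shown by one test. An injury as bad or worse that comes to light another way leaves continued enrolment to case-by-case judgement. A fistula is the clearest example, because by the protocol's own account it can appear after the only scheduled swallow. At stake is whether further patients are treated with the device while a serious esophageal injury is being reviewed.

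**Working it through.** **Coverage, from the text**

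| Event | Does section 7.2 require a stop? | What else applies |
|---|---|---|
| Laceration on a swallow, scheduled or later | Yes | – |
| Perforation on a swallow | Plausibly yes, as a laceration | – |
| Laceration or perforation confirmed only by CT, endoscopy or clinical presentation | No | Oversight, causality assessment, IRB reporting |
| Atrio-esophageal fistula | No | The same; it is a serious adverse event if it "results in a fatality or is life threatening" |

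The gap is the last two rows. It depends on no number. The plan gives no operating figure for the stopping rule, so there is none to reproduce.

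**Fistula.** Inputs: background rate 0.04% (section 4) and a maximum of 64 patients (section 6.1).

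1 − (1 − 0.0004)^64 = 0.0253, or 2.5%.

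**Laceration or perforation.** Section 4 states "The esophagus was successfully displaced using the DV8 retractor in over 200 patients worldwide" and "No complications have been reported with its use". Taken as 0 in 200, the one-sided 95% upper limit is 1 − 0.05^(1/200) = 0.0149, or 1.5%. The documents do not say that those patients were systematically imaged.

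I assume an injury rate r of 0.5% or 1%. Both fit 0 in 200: 0.995^200 = 0.37 and 0.99^200 = 0.13. So would a rate near zero. I also assume that a share f of injuries, 70% or 90%, shows on the swallow.

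- Current rule fires: 1 − (1 − rf)^64
- At least one injury occurs and the current rule never fires: (1 − rf)^64 − (1 − r)^64
- Any laceration, perforation or fistula occurs, taking the two risks as independent: 1 − (1 − r)^64 × (1 − 0.0004)^64

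| r | f | Current rule fires | Injury occurs, rule never fires | Any such event occurs | Last minus first |
|---|---|---|---|---|---|
| 0.5% | 90% | 25.1% | 0.749 − 0.726 = 2.4% | 29.3% | 4.2 points |
| 0.5% | 70% | 20.1% | 0.799 − 0.726 = 7.3% | 29.3% | 9.2 points |
| 1% | 90% | 43.9% | 0.561 − 0.526 = 3.5% | 48.8% | 4.8 points |
| 1% | 70% | 36.2% | 0.638 − 0.526 = 11.2% | 48.8% | 12.6 points |

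At a rate of 0.1% the fourth column falls to 0.6% (f = 90%: 0.9440 − 0.9380) or 1.8% (f = 70%: 0.9562 − 0.9380).

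**Why these are upper bounds for a wider rule.** The last three columns count injuries that occur. A rule that stops on confirmed injury acts only on those that are found. The swallow is the only scheduled imaging of the esophagus after the procedure, CT follows only a visualized injury, and the telephone scores record symptoms. Without a new test, a swallow-negative injury is found only if it causes symptoms or is otherwise worked up.

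**The case against.** The strongest reply is that this is a deliberate, strict choice. One case is enough, every patient has the same test, and that test is also a safety endpoint. Once swallow-visible perforations are counted, little is left uncovered. Only the fistula rate comes from the documents. It is small, it is a background rate for radiofrequency ablation, and section 4 attributes esophageal injury to heat, so a fistula may not come from the deviation at all. Attribution, oversight and IRB reporting already exist. Confirmation by any method would make the trigger depend on unscheduled work-up, and a minor tear found by chance could end the study.

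Much of this stands. The gap is narrow, its size for laceration and perforation rests on assumptions, and the minor-tear risk is a real cost. The possible ablation origin of a fistula argues for a pause, not a stop. What does not follow is that oversight closes the gap: no section ties a fistula, or an injury confirmed another way, to a halt.

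A reader might infer several stronger points, and the documents support none of them:

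- *That the study could not be halted for these events.* Sections 9.3 to 9.3.5 leave that open to the investigator and the IRB.
- *That perforation is wholly outside the rule, or that the rule expires at day 3.* A perforation on the swallow would plausibly count, and section 7.2 sets no day.
- *That existing follow-up already confirms every missed injury, so 2.4% to 11.2% are extra stops.* Telephone symptom scores do not confirm a laceration.

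**Conclusion.** The point holds as a gap in a pre-specified rule, not as an absence of safety oversight. Confidence in the textual reading is high; confidence in the size is limited. The one figure based on a documented rate is the 2.5% chance of at least one fistula in 64 patients. The 2.4% to 11.2% range for laceration or perforation rests on assumed rates of 0.5% to 1% and assumed visibility of 70% to 90%. The plan does not contradict itself here. This is a cheap improvement that applies the sponsor's own one-case standard to injuries of equal or greater gravity.

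**What to change.** Reword section 7.2 to read:

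> Enrolment stops on one or more esophageal lacerations or perforations confirmed by any method, and pauses pending causality review (section 9.3.4) and IRB notification on any atrio-esophageal fistula, at any time up to the 3-month contact.

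The pause lets the review that section 9.3.4 already requires separate ablation from deviation before enrolment resumes.

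The cost is one sentence, with no new test or visit. The chance of a stop or pause rises by at most about 4 to 13 percentage points in total under the assumptions above, and by less where swallow-negative injuries go unfound. This includes a possible stop for a minor tear found by unscheduled work-up, which the sponsor should accept knowingly. Under those assumptions, most of the chance of stopping already comes from the existing one-case rule.

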8 PATIENT ENROLLMENT AND WITHDRAWAL

Patients meeting the study inclusion criteria will be identified in the outpatient setting by one of the study staff.

The study will typically be described (including the risks and benefits) during the clinic visit. Consent will typically be obtained at the time of the initial assessment if it is clear that the patient truly understands the nature of the study. Alternatively, the patient will be allowed to take a copy of the consent form home to contemplate whether they would like to be enrolled in the study. Only patients who voluntarily provide consent will be included in this study. Consent will be obtained prior to undergoing the ablation procedure. Patients will be able to withdraw from the study at any point without compromising their medical care.

Since there is minimal additional follow-up beyond routine clinical care in this study, we expect to achieve > 95% rate of follow-up.

9 STUDY PROCEDURES

All aspects of the study (including pre- and post- care) are currently undertaken during the care of patients undergoing traditional catheter ablation procedures for AF.

9.1 PRE- AND ABLATION PROCEDURE

9.1.1 PRE-PROCEDURE TESTING

The following tests and procedures will occur before the ablation:

- Baseline swallowing impairment score
- Collect any pre-procedural imaging of left atrium (if performed): MRI/CT within 6 months of procedure
- Baseline CBC-Platelets, PTT/PT-INR

9.1.2 ABLATION PROCEDURAL DETAILS

- Patients will be brought to the electrophysiology laboratory in a fasting state.
- General anesthesia will be used for all cases, which is routine practice for all AF ablations at MGH.
- Venous ± arterial access, number of transseptal punctures performed, and catheter selection (coronary sinus catheter, right atrial catheter, intra-cardiac echocardiography (ICE), and ablation catheter) will be left to the discretion of the operator.
- Any 3D Mapping system can be used
- Any thermal based ablation system can be used for the procedure.
- Insertion of the DV8 tool will be performed at the beginning of the procedure. The esophagus will be then moved with a goal of deviation of 2 cm from the ablation sites.
- Circumferential pulmonary vein (PV) isolation will be performed next.
- Bidirectional block in and out of the PV must be demonstrated after PV isolation (again, this is usual clinical practice).
- Use of adenosine to assess for dormant conduction is required.
- Per usual practice of the clinical site, Isoproterenol may be used at the end of the study protocol to assess for PV reconnection
- After performance of PV isolation on both sides additional LA ablation is left to the discretion of the electrophysiologist

9.2 POST-PROCEDURE

9.2.1 POST-PROCEDURE TESTING

- Swallowing impairment score: next morning

- Preferably the next day but up to 3 days after the procedure: Barium swallow to be performed on all patients.

9.2.2 POST-PROCEDURE FOLLOW UP

- 2 week and 3-month phone follow up: Repeat swallowing impairment score (to be obtained trans-telephonically)

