Thermal injury during AF ablation can occur in the form of esophageal erythema, hemorrhage, erosions, ulceration, gastro-esophageal motility disorders or rarely atrio-esophageal fistulas. These occur consequent to the use of thermal based ablation applied to the posterior wall that often lies immediately adjacent to the esophagus (9,10). It is thought that this thermal energy extends beyond the posterior LA wall and reaches the adjacent esophagus causing damage that manifests as described above. In patients undergoing radiofrequency (the most common thermal based energy source) catheter ablation of AF, the reported incidence of any esophageal injury varies from 2.2% - 48%. The incidence of the often catastrophic atrio-esophageal fistula however, is much lower at around 0.04% (11). Typically, the clinical presentation of such fistulae occurs late after the procedure (usually within the first 2 weeks) (9,10). The symptoms are usually nonspecific, including fever, neurological abnormalities, gastrointestinal bleeding, and sepsis. This condition is often fatal. The mechanism of esophageal injury is thought to be to thermal injury (9,10,12,13). The degree of variation in the reported incidence of esophageal damage (2.2- 48%) is likely accounted for by differences in the frequency of use of esophageal protection (e.g. - temperature monitoring probe), use of general anesthesia versus conscious sedation, magnitude of power, duration and contract force during ablation and finally the method of assessment of esophageal injury. An effective strategy to reduce gastro-esophageal injury is therefore of significant clinical importance.

[figure not shown]

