Appendix 1:

Swallowing Impairment Score			COMMENT	
SYMPTOMS	Min/ None	Mild	Mod	Severe
Throat pain/discomfort				
Effort required to swallow				
Pain during swallowing				
SYMPTOMS	Never	Some-times	Often	Always
Coughing while swallowing				
Sensation of foreign-body in my throat				
I notice a change in my voice				
Bleeding				
Vomiting				
Nausea				
Abdominal Pain				
Other, specify: _____				

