- Ensure all consents are signed and patient meets inclusion/exclusion criteria
- Baseline Swallowing impairment score
- After induction of general anesthesia, the DV8 tool will be inserted.
- PV isolation will be performed after the deviation of the esophagus.
- Baseline esophageal position (record (cine) straight AP view) to be identified with contrast in the esophagus. Exclude from deviation if esophageal diverticulum is identified.
- After maximum possible deviation is performed, cine fluoroscopic view is to be acquired for both left sided and right-sided ablation.
- Care must be taken to ensure fluoroscopic images are acquired at the same level of magnification. Care must also be taken to ensure that the esophagus has sufficient barium at all times.
- Esophageal LET probe must be manipulated to approximate catheter tip at all times during any posterior wall ablation: Note: All posterior wall lesions are to be recorded:
 - Duration of lesion
 - Power delivered for all lesion

Esophageal deviation and data collection:

- Extent of esophageal deviation measured on the electroanatomic mapping system as the distance between the ablation line and the trailing edge of the esophagus. The trailing edge of the esophagus will be delineated on the EAM system guided by fluoroscopy.
- Time from first ablation to last ablation for PV isolation for all four veins.
- From start of deviation maneuver to last ablation for PV isolation.
- Total procedure duration
- Total Fluoroscopy time
- Confirm PV isolation at 30 minutes, record if vein reconnects.
- All non-PV ablation should be performed after PV isolation only. Above parameters should be recorded if additional deviation is performed for non-PV ablation such as CFE or atrial tachycardia ablation.
- Obtain all Fluoro/cine images and electroanatomic mapping data.

Post-procedural care

- Next morning; Administer SIS symptom scale and record score
- Barium swallow.

Outpatient follow- up

- 2 weeks/ 3 months – Telephonic assessment of Swallowing Impairment Score
- Any further follow up that may be relevant to complications during the procedure

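### After day 3 the only scheduled contacts repeat a swallowing form that does not prompt for fever, neurological symptoms or hospital care, so late safety events are not uniformly ascertained

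*Combined protocol and SAP*

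**What the plan says.** On timing, section 4 states: "Typically, the clinical presentation of such fistulae occurs late after the procedure (usually within the first 2 weeks". On presentation: "The symptoms are usually nonspecific, including fever, neurological abnormalities, gastrointestinal bleeding, and sepsis". It adds that the condition is often fatal, and on frequency it says: "The incidence of the often catastrophic atrio-esophageal fistula however, is much lower at around 0.04" (the figure is a percentage).

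Section 9.4 names the event among the risks specific to this protocol: "Atrio-esophageal fistula- An abnormal connection between the atria of the heart and the esophagus in which they fuse together". Infection is in the same list. Stroke and pneumonia or sepsis are in the separate list of risks of a standard ablation.

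The last scheduled test is in section 9.2.1: "Preferably the next day but up to 3 days after the procedure: Barium swallow to be performed on all patients". Section 9.2.2 then gives the whole of later follow-up: "2 week and 3-month phone follow up: Repeat swallowing impairment score (to be obtained trans-telephonically". The work flow in Appendix 2 agrees, describing the 2-week and 3-month contacts as "Telephonic assessment of Swallowing Impairment Score".

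The form in Appendix 1 has items such as "Sensation of foreign-body in my throat". Section 9.3 links the score to symptoms, including dysphagia, that may follow manipulation of the esophagus.

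**The concern.** The study's stated aim is feasibility and safety. The protocol itself describes the gravest esophageal harm as appearing after the imaging window, mostly through symptoms that have nothing to do with swallowing. The scheduled contacts that cover that period use an instrument built for a different purpose.

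Whether a fever, a transient neurological episode or an admission elsewhere reaches the study record then depends on whether the patient thinks to mention it. Nonspecific symptoms are easily left unlinked to an ablation some days earlier. The same applies to stroke, infection and pneumonia or sepsis, all of which section 9.4 lists. What is at stake is the completeness and evenness of the late safety data, and how much weight an absence of such events in the report can carry.

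**Working it through.** The main check is a comparison of texts. The plan states no figure on this point to reproduce.

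**1. Scheduled contacts after the procedure** (sections 9.2.1 and 9.2.2, Appendix 2)
- Next morning: swallowing score.
- Next day, up to day 3: barium swallow.
- 2 weeks: telephone swallowing score.
- 3 months: telephone swallowing score.

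Nothing is scheduled between day 3 and week 2, a gap of 14 − 3 = 11 days. That is most of the window in which section 4 says fistula usually presents. The 2-week call falls at the end of the window.

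**2. Presenting features in section 4 against the named items in Appendix 1**
- Fever: no item.
- Neurological abnormalities: no item.
- Gastrointestinal bleeding: covered by a general bleeding item.
- Sepsis: no item.

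The other nine named items are throat pain, swallowing effort, swallowing pain, cough on swallowing, foreign-body sensation, voice change, vomiting, nausea and abdominal pain. A free-text Other line follows. So one of the four features is prompted. This is a description, not a measure of sensitivity: the section 4 list is open-ended, and sepsis is a diagnosis that overlaps with fever.

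**3. Other routes into the record**
- Section 9.3: patients report symptoms to study staff during follow-up. No timing or symptom list is given.
- Section 9.3.1: an adverse event is any unwanted clinical event, related or not.
- Section 9.3.3: adverse events are captured throughout participation.
- Appendix 2: further follow-up as relevant to complications during the procedure.
- Appendix 1: the Other line.

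All of these can accept a late event. None asks about one at a set time. The definition of a serious event in section 9.3.2 does not name hospital admission, so an admission is not an explicit trigger either.

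**4. Size** (inputs: 0.04% from section 4; 64 patients from sections 6.1 and 7.1)
- Expected fistulas: 64 × 0.0004 = 0.0256.
- Chance of at least one: 1 − (1 − 0.0004)^64 = 0.0253, or 2.5%.
- Exact one-sided 95% upper limit if none is seen: 1 − 0.05^(1/64) = 0.0457, or 4.6%. The upper end of the two-sided 95% interval is 1 − 0.025^(1/64) = 0.0560, or 5.6%.

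The 4.6% limit is about 114 times the assumed rate (0.0457 / 0.0004). With perfect ascertainment, 64 patients would still say almost nothing about the fistula rate. The value of better questions lies in complete individual records.

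**The case against.** The strongest reply is that adverse event capture does not run through the swallowing score. Section 9.3.1 defines an adverse event very broadly, section 9.3.3 captures events throughout participation, section 9.3 provides for self-report, and the form ends with an open line. A reader might infer that a patient with a fever on day 12 who scores clean on the form would be recorded as event-free. The documents do not support that: no rule equates a clean score with the absence of adverse events. This part of the reply stands, and it limits the point to the lack of a scheduled prompt.

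A reader might also infer that section 9.3.3 relies on a list of protocol-defined events that was never written. The phrase can as naturally mean events that meet the definitions in sections 9.3.1 and 9.3.2, so nothing is built on it here.

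It can further be said that no late-injury endpoint exists. The only esophageal safety endpoint is laceration on the barium swallow at 1 to 3 days (section 5.2), the stopping criterion in section 7.2 uses the same finding, and the score was never meant to detect fistula. That is correct, and no planned analysis is compromised. It does not remove the mismatch: the study claims a safety aim, lists fistula and infection as risks specific to the protocol, and makes two late calls that do not ask about their main features.

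Lastly, questions at 2 weeks come too late to bring much earlier recognition of an event that usually presents within 2 weeks. This also stands.

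**Conclusion.** The point holds as a gap in prompted, uniform ascertainment of late safety events. After day 3 the two scheduled calls prompt for one of the four presenting features that the protocol names, and not for fever, neurological symptoms or hospital care.

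It should not be read as a failure of all adverse event reporting, or as undermining a planned claim of no late injury: the plan makes no such claim. The primary endpoint, sample size and power are untouched. At the protocol's own rate, 0.026 fistulas are expected in 64 patients, with a 2.5% chance of any.

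The practical benefit is more complete recording of late events, including the infection, stroke and pneumonia or sepsis risks in section 9.4, for which the documents give no rates. Any gain in early recognition is small.

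The conclusion assumes that Appendix 1 is the whole call script, as section 9.2.2 and Appendix 2 indicate, and that the 0.04% figure applies to this population. It is worth correcting because the correction is cheap, but it does not threaten the study's main result.

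**What to change.** In section 9.2.2 and Appendix 2, add three fixed yes/no questions to both the 2-week and the 3-month call:

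1. Fever or chills since the last contact.
2. New neurological symptoms since the last contact.
3. Any emergency visit or hospital stay since the last contact.

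The investigator should assess each yes against the definitions in sections 9.3.1 and 9.3.2 and the causality categories in section 9.3.4. A yes should not become an adverse event automatically, because section 9.3.1 excludes unchanged pre-existing conditions and a planned admission would otherwise be counted. Report the answers, with the number of patients reached at each call, alongside the safety results.

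The change concerns data capture only. Clinical action on any answer stays with the study team.

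The cost is three lines on calls already scheduled, with no new visit or test, and a few extra reports to review. The change does not fill the interval between day 3 and week 2, and the report should not imply that it does.
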